### 7.3.2 Analysis

Changes from baseline for laboratory tests to visits in the DB+SB part will be summarized using descriptive statistics by visit and treatment group (in the DB part). Changes from DB-WD baseline (Week 36) to visits in the DB-WD part and up to EOS will be summarized by visit and treatment group (in the DB-WD part). Data will be displayed in SI units whenever possible and graphical approaches will be applied for certain variables.

Percentage changes from baseline in plasma volume to visits in the DB+SB part will be estimated based on baseline (V4) as well as post-baseline (Vx) in hemoglobin and hematocrit (as a fraction between 0 and 1) using the following formula [[Strauss 1951](#)]:

$$\text{estimated change} = 100 \times \frac{\text{hemoglobin (V4)}}{\text{hemoglobin(Vx)}} \times \frac{1 - \text{hematocrit (Vx)}}{1 - \text{hematocrit(V4)}} - 100$$

Percentage changes from Week 36 (V11) in plasma volume to visits in the DB-WD part will be estimated similarly but with V4 replaced by V11. Estimated changes in plasma volume will be summarized by visit and treatment group (in the DB+SB part or DB-WD part, where appropriate).

The number (%) of subjects with laboratory marked abnormalities will be tabulated by study part (DB, SB, and DB-WD) and treatment group (within study part). In addition, the number (%) of subjects with AST or ALT > 3 × the ULN combined with bilirubin > 2 × ULN will be tabulated. In addition, AST or ALT > 5 or 10 × ULN will also be tabulated.

## 7.4 Electrocardiography

### 7.4.1 Variables

A standard 12-lead ECG is performed as defined in the schedule of assessments [[Table 1](#) and [Table 2](#)]. ECG data will be electronically transferred from the ECG laboratory database to Idorsia and will not be (re-)calculated.

The following variables will be evaluated: HR (bpm), PR (ms), QRS (ms), QT (ms), QTcB (ms), and QTcF (ms). Note that HR will be evaluated only in the context of the ECG. For vital signs, pulse rate will be used based on assessment done during AOBPM.

ECG abnormalities are defined as follows:

- QTcF (Fridericia's formula) maximum value > 450 ms, > 480 ms, or > 500 ms;
- Maximum increase from baseline in QTcF (Fridericia's formula) > 30 ms, > 60 ms.

All assessments (including the unscheduled ones) are considered and re-assigned to the most appropriate visit according to the visit windows described in [Section 10.1.2](#).

## 7.4.2 Analysis

Descriptive statistics by study part (DB+SB and DB-WD), visit and treatment group (within study part) will be provided for observed values and absolute changes from baseline (or DB-WD baseline (Week 36), where appropriate) in numeric 12-lead ECG values (HR, PR, QRS, QT, QTcB, QTcF).

The number (%) of subjects with treatment-emergent ECG abnormalities will be summarized by study part (DB, SB, and DB-WD), visit and treatment group (within study part). These are presented cumulatively, e.g., a QTc value of 501 ms is reported in the > 450 ms (H), > 480 ms (HH) and > 500 ms (HHH) categories; the same applies to abnormalities related to changes from baseline (or Week 36, where appropriate).

ECG findings will be summarized by study part (DB, SB, and DB-WD) and treatment group (within study part).

## 7.5 Vital signs and body weight

### 7.5.1 Variables

Body weight and pulse rate (this term is used to distinguish it from heart rate measured by ECG) are assessed according to the schedule of assessments [Table 1 and Table 2]. Pulse rate is measured simultaneously with AOBPM and the average of four readings (calculated by the vendor) will be used in the analysis. All assessments (including the unscheduled ones) are considered and re-assigned to the most appropriate visit according to the visit windows described in Section 10.1.2.

### 7.5.2 Analysis

Descriptive statistics by study part (DB+SB and DB-WD), visit and treatment group (within study part) will be provided for observed values as well as absolute changes from baseline to each visit in the DB and SB parts and from DB-WD baseline (Week 36) to each visit in the DB-WD part and up to EOS for body weight and pulse rate.

## 7.6 Other safety variables and analyses

### 7.6.1 Treatment-emergent MACE and MACE-plus

MACE is defined as cardiovascular death, non-fatal myocardial infarction, or non-fatal stroke. MACE-plus includes, in addition, hospitalization for heart failure. The analyses will focus on MACE-plus.

Treatment-emergent MACE-plus events confirmed by the CAC are reported on the **Consensus Event Adjudication Form**. The number (%) of subjects with confirmed MACE-plus and sub-categories (i.e., death, non-fatal myocardial infarction, non-fatal stroke, or hospitalization for heart failure) will be tabulated by study part (DB, SB aprocitentan, or DB-WD) and treatment group (within study part). MACE-plus will be summarized by CKD stage at Baseline.

If there are *at least 12* subjects with an adjudication confirmed MACE-plus, the time from Randomization to (first) MACE-plus in the DB or SB aprocitentan part will be summarized by treatment group using Kaplan-Meier plots (supplemented by a table displaying the numbers of subjects at risk, with an event and censored by treatment group, using weekly intervals). For subjects without MACE-plus, the time will be censored at the last dose of DB or SB treatment (whichever comes last). Additionally, a ‘two-step’ Cox model with a factor for treatment will be fitted [see Section 8.2 for details].

If there are *at least 12* subjects with an adjudication confirmed MACE -plus, the time from Re-randomization to (first) MACE-plus in the DB-WD part will be summarized similarly, except that the Cox model is the conventional one. For subjects without MACE-plus, the time will be censored at the last dose of DB-WD treatment + 30 days (or EOS date, whichever comes first).

For each treatment group, exposure-adjusted MACE-plus incidence rates will be provided per 100 subject-years. The exposure-adjusted incidence rate is calculated as the total number of subjects who experienced the MACE-plus event, divided by the total subject-time at risk during each study part. For subjects who had the MACE-plus event while on study treatment, subject-time at risk is the time from start date of study treatment to date of first event in the respective study part. For subjects who did not experience the MACE-plus event, subject-time at risk is the duration of study treatment in the respective study part. The total subject-time at risk is the sum of all the subject-times at risk. These tables will include the total number of subjects, the total subject-years on study, the total subject-years at risk per event, and the incidence rate (number of subjects with the event / total subject-years at risk for the event  $\times$  100). An exact 95% CI will be constructed based on the Poisson distribution.

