## 5.5 Study treatment duration and compliance

### 5.5.1 Treatment duration

Randomized treatment duration (in days) is defined separately for the DB, SB aprocitentan and DB-WD parts as the date of the last dose of treatment in the DB (SB aprocitentan, DB-WD, respectively) part minus the date of the first dose in the DB (SB aprocitentan, DB-WD, respectively) part plus one day, ignoring treatment interruptions. The detailed derivations based on the **Study Treatment Log** are given in Section 10.1.1. Randomized treatment duration will also be expressed in weeks.

RI treatment duration is defined as the date of the last dose of SB placebo minus the date of the first dose of SB placebo plus one day [see Section 10.1.1].

Standardized background antihypertensive therapy duration in the RI period as well as in the DB, SB aprocitentan, and DB-WD parts is defined similarly based on the **Standardized Background Antihypertensive Therapy Log**.

Treatment duration (in days as well as weeks) will be summarized by study part and treatment group (within study part) in the SAF, rSAF and mSAF, respectively. Total exposure (in subject-years, where a year equals 365.25 days) will also be summarized by study part and treatment group.

Time from first dose of DB treatment to (premature) treatment discontinuation in the DB or SB aprocitentan part will be summarized by treatment group using Kaplan-Meier plots (supplemented with a table displaying the numbers of subjects at risk, with an event, and censored by treatment group, using weekly intervals) in the SAF. For subjects who completed the treatment, time to discontinuation will be censored at the last dose of SB treatment (or at the last dose of DB treatment if the subject did not enter the SB part). Additionally, a ‘two-step’ Cox model with a factor for treatment in the DB part will be fitted. This model allows for different treatment effects in the DB and SB aprocitentan parts. The treatment effect in the latter part (if any) is expected to be smaller than in the former part [for details, see Section 8.2].

Time from first dose of DB-WD treatment to (premature) treatment discontinuation in the DB-WD part will be summarized similarly in the mSAF, except that the Cox model is the conventional one.

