### 7.1 Adverse events

#### 7.1.1 Variables

##### 7.1.1.1 Treatment-emergent adverse events

The original terms used by the investigators to describe AEs in the **Adverse Events** eCRF are assigned a PT and a SOC for classification and tabulation using MedDRA (last available version).

Subjects who experienced the same AE more than once within a specified time period (as qualified by the same PT) are counted only once.

An event/assessment is treatment-emergent if the onset/assessment date is between the start date of the randomized treatment period up to EOT+30 days (begin and end dates included). More in particular:

- An event/assessment is DB treatment emergent if the onset/assessment date is between the start date of the DB part up to the day before the start date of the SB treatment part (or EOT + 30 days if the subject did not enter the SB part);

- An event/assessment is SB treatment emergent if the onset/assessment date is between the start date of the SB aprocitentan part up to the day before the start date of the DB-WD treatment part (or EOT + 30 days if the subject did not enter the DB-WD part);
- An event/assessment is DB-WD treatment emergent if the onset/assessment date is between the start date of the DB-WD part up to EOT + 30 days.

An event/assessment with an onset/assessment date between the start date of the run-in period up to the start of randomized treatment period (if the subject is randomized; EOT if the subject is not randomized) will be designated as run-in-emergent.

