### 7.1.2 Analysis

An overview table will be provided displaying by study part (DB, SB aprocitentan or DB-WD) and treatment group (within each study part) the number (%) of subjects with at least one treatment-emergent: AE, SAE, AE leading to premature discontinuation of study treatment, AESI, MACE and MACE-plus (the latter two as confirmed by adjudication).

A similar overview table (but without study part and treatment group) will also be provided for run-in-emergent AEs based on the RIS.

Treatment-emergent AEs will be tabulated by study part (DB, SB aprocitentan or DB-WD), and treatment group (within each study part), SOC and PTs within each SOC: the number and percentage of subjects who experienced at least one AE, at least one AE within each SOC and at least one AE within each PT will be displayed. AEs will also be summarized by decreasing frequency of PT in the aprocitentan 25 mg group.

A similar table (but without study part and treatment group) will also be provided for run-in-emergent AEs based on the RIS.

AEs will also be tabulated by maximum intensity and relationship to aprocitentan or placebo. Relationship to standardized background antihypertensive therapy will only be listed.

If an AE starts in one study part and ends in the next part without increasing intensity, it is counted only in the first part.

Treatment-emergent SAEs will be summarized in a similar manner as AEs.

For EudraCT purposes, non-serious and total death / serious AEs will be summarized separately by study part.

AEs leading to premature discontinuation of study treatment will be summarized in a similar manner as AEs. AESI (except hepatic disorders) will be summarized by CKD stage at Baseline.

The time from Randomization to (first) oedema / fluid retention AESI in the DB or SB aprocitentan part will be summarized by treatment group using Kaplan-Meier plots (supplemented by a table displaying the numbers of subjects at risk, those with an event, and those censored by treatment group, using weekly intervals). For subjects without oedema / fluid retention, the time will be censored at the last dose of DB or SB treatment, whichever comes last. Additionally, a 'two-step' Cox model with a factor for treatment will be fitted [see Section 8.2 for details].

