### 10.1 Analysis periods and visit windows

#### 10.1.1 Analysis periods

The **screening period** is defined as the time from the informed consent date until one day before the run-in period start date (or EOS if the subject does not enter the run-in).

The **RI period** begins at the date of the first dose of RI treatment and ends at the date of the last dose of RI treatment, collected on the **Study Treatment Log** where ‘Study Period’ is ‘Single Blind Run-in’.

The **randomized treatment period** begins at the DB treatment start date and ends at the *last* of the treatment stop dates collected on the **Study Treatment Log** where ‘Study Period’ is not ‘Single Blind Run-in’ and the reason for treatment end is not ‘Interruption due to an AE’ or ‘Interruption not due to an AE’.

The randomized treatment period is divided into three parts: DB, SB aprocitentan and DB-WD.

- The DB part begins at the DB treatment start date and ends at the DB treatment stop date collected on the **Study Treatment Log** where ‘Study Period’ is ‘Double-Blind Treatment (Part 1)’ and the reason for treatment end is not ‘Interruption due to an AE’ or ‘Interruption not due to an AE’.
- The SB aprocitentan part begins at the SB treatment start date and ends at the SB treatment stop date collected on the **Study Treatment Log** where ‘Study Period’ is ‘Single-Blind Treatment (Part 2)’ and the reason for treatment end is not ‘Interruption due to an AE’ or ‘Interruption not due to an AE’.
- The DB-WD part begins at the DB-WD treatment start date and ends at the DB-WD treatment stop date collected on the **Study Treatment Log** where ‘Study Period’ is ‘Double-Blind Withdrawal Treatment (Part 3)’ and the reason for treatment end is not ‘Interruption due to an AE’ or ‘Interruption not due to an AE’.

Should there be any ‘gap’ between the end of one period and the start of the next, then the gap days are allocated to the former period. In the unlikely case that the gap is more than 30 days, gap days 31, 32, etc. will not be allocated to a study part.

The **safety FU period** begins one day after the end of the randomized treatment period and ends at the date of the EOS visit. Safety data obtained during the safety FU period or at the EOS visit will be allocated to the last part of the subject’s randomized treatment period. This is restricted to data collected up to EOT+30 days. Safety data collected beyond that time point will not be allocated to a study part.

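### The MACE-plus incidence rate counts events over a longer window than its time at risk, and has no rule for a first event after the last dose

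*SAP*

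**What the plan says.** **Numerator.** SAP Section 7.6.1 defines the rate as "the total number of subjects who experienced the MACE-plus event, divided by the total subject-time at risk during each study part". That sentence has no on-treatment limit. The section is headed as treatment-emergent MACE and MACE-plus, and the overview table in Section 7.1.2 likewise shows "the number (%) of subjects with at least one treatment-emergent: AE, SAE, AE leading to premature discontinuation of study treatment, AESI, MACE and MACE-plus".

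**Event window.** Section 7.1.1.1 makes an event DB-WD treatment-emergent if its "date is between the start date of the DB-WD part up to EOT + 30 days". For the DB part the window closes the day before SB treatment starts, "or EOT + 30 days if the subject did not enter the SB part"; the SB part has the matching rule. Section 10.1.1 agrees: "Safety data obtained during the safety FU period or at the EOS visit will be allocated to the last part" of the subject's randomized treatment, up to EOT + 30 days.

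**Time at risk.** Section 7.6.1 gives two rules. With an event: "For subjects who had the MACE-plus event while on study treatment, subject-time at risk is the time from start date of study treatment" to the first event in that part. Without one: "For subjects who did not experience the MACE-plus event, subject-time at risk is the duration of study treatment in the respective study part". Section 5.5.1 defines that duration as "the date of the last dose of treatment in the DB (SB aprocitentan, DB-WD, respectively) part minus the date of the first dose", plus one day, so it stops at the last dose.

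**Time-to-event analysis of the same endpoint.** Also in Section 7.6.1, event-free subjects in the DB-WD part are censored 30 days after the last DB-WD dose, or at EOS if earlier. In the combined DB+SB analysis they are censored at the last dose. Section 7.1.2 uses the same two rules for oedema / fluid retention.

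**The concern.** A subject whose first MACE-plus falls in the 30 days after the last dose meets the treatment-emergent definition and is tabulated in Section 7.6.1. That subject fits neither time-at-risk rule: the event did not occur on treatment, and the subject is not event-free. I found no other section that settles the case, so two programmers following the SAP could report different rates.

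If the event is counted, event-free subjects are followed for it for 30 days that the denominator leaves out. The mismatch is largest in the DB-WD part, where nearly every subject has the 30-day tail. In the DB and SB parts only subjects who do not continue have it.

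At stake are absolute cardiovascular event rates in a trial with long-term safety over 48 weeks as a secondary objective (SAP Section 3.2).

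**Working it through.** The documents give no MACE-plus rate or event count, so there is no stated figure to reproduce.

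**Inputs from the SAP**
- DB-WD treatment: 12 weeks = 84 days (Section 2.1). Tail: 30 days. Table 6 agrees: 84 + 30 = 114, the EOS target WD day.
- DB part: 4 weeks = 28 days. SB part: 32 weeks = 224 days.
- Planned numbers: 600 randomized, 380 re-randomized 1:1 (190 per arm), 300 completing. Actually randomized: 730.

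**Assumptions (not in the documents):** the hazards, early-stop shares and follow-up shares used below.

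**1. DB-WD, post-dose events counted**
- Events accrue over 114 days and time over 84: 114/84 − 1 = **35.7%**. A true 2.0 per 100 subject-years is reported as 2.0 × 114/84 = 2.7.
- Exact exponential expectations at 1 to 10 per 100 subject-years give 35.0% to 35.7%.
- With 300 of 380 completing and the other 80 stopping on average at day 42, mean exposure is (300 × 84 + 80 × 42)/380 = 75.2 days. The excess is 30/75.2 = 40% if all are followed for 30 days, and (300/380) × 30/75.2 = 32% if those who stop early are not followed.
- If the off-treatment hazard is *r* times the on-treatment hazard, the excess over the on-treatment rate is *r* × 30/84: 18% at *r* = 0.5, 36% at *r* = 1, 71% at *r* = 2.

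**2. DB-WD, on-treatment events only**
- Events and time both cover 84 days, so inflation is 0%.
- Under constant hazard the rate omits 30/114 = **26%** of the treatment-emergent DB-WD events tabulated in the same section.

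**3. DB and SB, post-dose events counted**

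With share *p* not continuing and stops spread evenly over a part of length *L*, inflation is 30*p* / [*L*(1 − *p*/2)].
- DB (*L* = 28): 2.2% at *p* = 0.02, 11.3% at *p* = 0.10.
- SB (*L* = 224): 0.7% at *p* = 0.05, 6.0% at *p* = 220/600 = 0.367. The last value is the planned loss placed wholly in SB; Section 2.1 says drop-out was lower than expected.

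**4. Between-arm ratio in DB-WD**

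With early stops of 5% and 15%, the inflation factors are 1 + 30/(84 × 0.975) = 1.366 and 1 + 30/(84 × 0.925) = 1.386. The ratio shifts by 1.386/1.366 − 1 = 1.5%.

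**5. Does the Poisson interval show the shift?**

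At 2.0 per 100 subject-years:

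| Per arm | Expected events in 114 days | Of which in the tail | Coverage of true rate, mismatched | Coverage, aligned |
|---|---|---|---|---|
| 190 | 190 × 0.02 × 114/365.25 = 1.2 | 0.3 | 97% | 99% |
| 365 (all 730 re-randomized) | 365 × 0.02 × 114/365.25 = 2.3 | 0.6 | 97% | 99% |

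At 12 expected events in one arm, mismatched coverage falls to 84% (aligned 96%). That needs 12/(365 × 114/365.25) = 10.5 per 100 subject-years with 365 per arm, or 20 with 190.

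**6. DB+SB hazard ratio, last-dose censoring**

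Take a true ratio of 1, low hazard, and events counted to 30 days after an early stop while the risk set ends at the last dose. I solved the Cox score equation separately in each interval.
- Early stop in DB/SB of 2%/10% in one arm and 5%/20% in the other: about 1.02 in both intervals.
- 2%/10% and 10%/20%: 1.04 in DB and 1.02 in SB.

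**The case against.** **The rate may be meant as on-treatment.** It is called exposure-adjusted, its event rule mentions only events on study treatment, and its event-free rule uses treatment duration. On that reading nothing is inflated. This stands as a possible reading, so a reader who infers that the DB-WD rate is definitely 36% too high goes further than the text allows. But the on-treatment phrase sits in the time-at-risk sentence, not the numerator sentence, and the section heading and the allocation rule in Section 10.1.1 point the other way. Even if accepted, it leaves a rate and a count for the same endpoint that disagree without a label.

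**The practical effect is small.** This stands. One or two events per arm are expected at 2.0 per 100 subject-years, and interval coverage stays at or above nominal. The 84% figure needs a rate five to ten times higher. The rates are descriptive.

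**A late rise in risk.** A reader might infer that setting the DB-WD rate beside the SB rate would make a constant hazard look like one. The arithmetic allows it under the counting reading, but the SAP plans no contrast between parts.

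**Related items.** A reader might extend the point to the diuretic endpoint in Section 7.6.2. The documents do not support it well: Section 5.4.4 defines study-concomitant therapy up to 30 days after EOT, Section 10.1.1 allocates follow-up safety data to the last part, and Table 5 lists only a Cox model. DB-WD censoring for lack-of-efficacy discontinuation in Section 6.5.2 concerns another endpoint and excess, not missing, risk time. The entry for all parts in Table 5 is a matter of labelling.

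**Conclusion.** The concern holds as a minor defect. Taken as written, the event window and the time at risk do not match, and a first event after the last dose has no rule. The DB-WD time-to-event analysis of the same endpoint already uses the longer period.

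- **If post-dose events count** (the better-supported reading), the overstatement in DB-WD is about 36%, resting on constant hazard, 84 days of treatment and full follow-up. Without constant hazard, the excess over the on-treatment rate is about 18% to 71% for an off-treatment hazard 0.5 to 2 times the on-treatment one.
- **If they do not count**, inflation is 0%, and about a quarter of the tabulated DB-WD events are left out unlabelled.

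The consequence is confined to descriptive absolute rates and their intervals; none of the three tested hypotheses is affected. Last-dose censoring in the DB+SB analyses of MACE-plus and oedema has the same cause and a smaller effect, about 2% to 4% on a hazard ratio under assumed drop-out differences. The MACE-plus model is fitted only if at least 12 subjects have an event.

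**What to change.** 1. **Preferred.** In Section 7.6.1, let time at risk in each part run from the start of the part to the earliest of first event, last dose + 30 days, EOS, or the day before the next part starts. This matches the existing DB-WD censoring.
2. **State that EOT in the treatment-emergent window means the last dose.** A footnote to Table 2 allows the EOT visit up to 7 days after the last dose following premature discontinuation, so a small mismatch could otherwise remain.
3. **Alternative to 1.** Restrict both numerator and denominator to on-treatment time, label the rate on-treatment, and footnote how many tabulated events it leaves out.
4. **DB+SB time-to-event analyses of MACE-plus and oedema.** For subjects who do not enter the next part, censor at the same limit as the one chosen for the rate.

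Cost: one or two SAP sentences and a change to derived time variables. No new data are needed.
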